### 10.2 Statistical Methods

### 10.2.1 General Methodology

All statistical analyses will be performed using the statistical software SAS® for Windows Version 9.4 or higher (SAS Institute, Inc., Cary, NC). In all calculations, zero will be substituted for concentrations below the quantification limit of the assay. Data collected from all randomized subjects will be presented in data listings. Both absolute values and change-from-baseline values

Statistical Analysis Plan

Project No. 200148 (Sponsor Study number ITF/2357/54)

for each subject will be given where applicable. All continuous data will be listed with the same precision as will be presented in the database. Data listings will be sorted by treatment, subject ID, and time point. Missing values will be represented by an empty cell and no imputation will be made.

For all descriptive statistics of continuous ECG parameters (i.e., HR, PR, QRS, and QTcF), data will be summarized including number of subjects (n), mean, median, standard deviation (SD), standard error (SE), 90% confidence interval (CI), minimum, and maximum by treatment and time point. For all modeling results of the by-time-point analysis of change-from-baseline values of continuous ECG parameters, n, least squares (LS) mean, SE, and 90% CI will be included. Modeling results of the by-time point analysis of placebo-corrected change-from-baseline will also include LS mean, SE, and 90% CI. Mean and median values will be rounded to the nearest tenth. SD, SE, and CI will be rounded to the nearest hundredth. For the concentration-QTc analysis, 2 decimal places will be shown for all effect estimates for all results which have an absolute value greater than 0.05. Each effect estimate with an absolute value  $\leq 0.05$  will be displayed with 2 significant figures. The CI of the effect estimate will display 1 more decimal place than the effect estimate. SE and P values will be reported with 4 digits and P values < 0.0001 will be reported as < 0.0001. Degrees of freedom (*df*), and t-value will be reported to the nearest tenth and nearest hundredth, respectively. Categorical data will be summarized 2 ways, by subject and by time point. Subject data will be summarized using the count of distinct subjects that fall into the category and the percentage of the total number of subjects. Time point data will be summarized using the count of the assessments that fall into the category and the percentage of the total number of assessments. Percentages will be rounded up or down to the next integer percentage. Population counts (either number of subjects or number of time points at the assessment) for each treatment group will be used as the denominator in the calculation of percentages unless otherwise specified

### 10.2.2 Baseline

For all continuous ECG parameters from each period, baseline is defined as the average of the measured ECG intervals from the 3 ECG time points (-45, -30, and -15 minutes) prior to treatment administration on Day 1 for the respective period. For T-wave morphology and U-wave presence in each period, baseline includes findings observed in any of the replicates from the 3 time points prior to dosing on Day 1 for the respective period.

### 10.2.3 QT Correction Methods

The QT and RR value for each beat will be used for HR correction.

The Fridericia's correction (QTcF) is defined as QTcF (ms) = QT (ms)/[RR(ms)/1000]1/3.

For evaluation of the HR-corrected QT interval, a scatter plot and quantile plot of QTcF and RR intervals by treatment with a regression line and a linear mixed-effects line (90% CI), respectively, also will be given.

#### Italfarmaco S.p.A.

#### 10.3 Analysis

#### 10.3.1 Concentration-QTc Analysis (Primary Analysis)

The relationship between plasma concentrations of ITF2357 and  $\triangle$ QTcF will be quantified using a linear mixed-effects modeling approach. The model will include  $\triangle$ QTcF as the dependent variable, plasma concentration of ITF2357 as the explanatory variate (0 for placebo), centered baseline QTcF (i.e., baseline QTcF for individual subject minus the population mean baseline QTcF for all subjects within the same treatment period) as an additional covariate, treatment (active = 1 or placebo = 0), time (i.e., nominal post-dose time point) as fixed effects, and random effects on intercept and slope per subject (Garnett et al).

An unstructured covariance matrix will be specified for the random effects. If convergence cannot be achieved even after appropriate rescaling of the concentrations, the random effect on the slope and intercept will be dropped, in this order, until convergence is achieved. The degrees of freedom (df) estimates will be determined by the Kenward-Roger method. From the model, the slope (i.e., the regression parameter for concentration ITF2357) and the treatment effect-specific intercept (defined as the difference between active and placebo) will be estimated together with the 2-sided 90% CL. The estimates for the time effects will be reported with df and SE.

The geometric mean of the individual  $C_{max}$  values for subjects in each of the active dose groups will be determined. The predicted effect and its 2-sided 90% CI for  $\Delta\Delta$ QTcF i.e., slope estimate × concentration + treatment effect-specific intercept) at this geometric mean  $C_{max}$  will be obtained. If the upper bound of the 2-sided 90% CI (equivalent to the upper bound of the 1-sided 95% CI) of the predicted QTc effect ( $\Delta\Delta$ QTcF is below 10 ms at clinically relevant plasma levels, it will be concluded that ITF2357 does not cause clinically relevant QTc prolongation within the observed plasma concentration ranges.

To evaluate the adequacy of model fit with respect to the assumption of linearity, the observed  $\Delta QTcF$  values adjusted by population time effect estimated from the model will be used. These individual placebo-adjusted  $\Delta QTcF_{i,k}$  ( $\Delta \Delta QTc_{i,k}$ ) values equal the observed individual  $\Delta QTcF_{i,k}$  for subject administered with ITF2357 or placebo at time point k minus the estimated population mean placebo effect at time point k (i.e., time effect). A quantile plot, i.e. plot of the quantiles (deciles) of observed ITF2357 concentrations and the mean placebo-adjusted  $\Delta QTcF$  ( $\Delta \Delta QTcF$ ) and 90% CI at the median concentration within each decile will be given. The regression line presenting the model-predicted  $\Delta \Delta QTcF$  (as described by Tornøe et al) will be added to evaluate the fit of a linear model and visualize the concentration-response relationship.

The SAS code for the concentration-QTc analysis is as follows.

PROC MIXED DATA=PKPD method=reml; CLASS SUBJID TIME;

11-JUN-2021 (Final 2.0)

Italfarmaco S.p.A.

MODEL DQTC=TRT CONC TIME CBASE/ solution cl noint alpha=0.1 alphap=0.1 COVB DDFM=KR; RANDOM INT CONC /type=UN SUBJECT=SUBJID s; RUN;

Where PKPD=PK/QTc population, SUBJID=subject number, TRT=treatment (active=1 or placebo=0), TIME=nominal post-dose time point, CONC=plasma concentration of ITF2357, CBASE=centered baseline QTcF, and DQTc= $\Delta$ QTcF.

Note: ESTIMATE statements will be included for the prediction of the effect in each of the active dose groups.

Italfarmaco S.p.A.

Statistical Analysis Plan Project No. 200148 (Sponsor Study number ITF/2357/54)

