### 3.5 Sample Size

It is planned to enrol up to 34 subjects to ensure 28 subjects with evaluable data.

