#### Italfarmaco S.p.A.

#### 10. Cardiodynamic ECG Assessment

### 10.1 ECG and Pharmacokinetic Sample Collection

The cardiodynamic assessment will be performed through 12-lead ECGs extracted from continuous recordings at prespecified time points, paired with PK samples.

Continuous 12-lead ECG recordings will be performed from 1 hour prior to dosing in each treatment period to 36 hours post-dose. At the ECG core laboratory, up to 10 replicate ECGs will be extracted at each of the following time points on Day 1 in each treatment period: 3 time points prior to dosing (-45, -30, and -15 minutes) and 0.5, 1, 1.5, 2, 2.5, 3, 3.5, 4, 5, 6, 7, 8, 12, 24, and 36 hours post-dose.

Subjects will be supinely resting for at least 10 minutes prior to and 5 minutes after each time point for ECG extractions, whenever possible. Subjects will be required to avoid postural changes during these ECG recordings.

The 12-lead Holter and ECG equipment will be supplied and supported by ERT. All ECG data will be collected using Global Instrumentation (Manlius, NY, USA) Ml2R ECG continuous 12-lead digital recorder. The continuous 12-lead digital ECG data will be stored onto SD memory cards. 12-lead ECGs will be extracted from the continuous recordings at pre-determined time points as defined in the study protocol, and will be measured centrally by ERT.

ECG intervals will be measured by the core laboratory in a blinded manner using the Early Precision QT technique (EPQT) (see Appendix A for more details). The ECG database will be locked before any statistical analysis is undertaken.

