### 10.4 Assay Sensitivity

The analysis to show assay sensitivity will be also based on the concentration-QTc analysis of the effect on  $\Delta\Delta$ QTcF of 400 mg oral moxifloxacin using a similar model as for the primary analysis. That is, the relationship between moxifloxacin plasma concentration and  $\Delta$ QTcF will be investigated by linear mixed-effects modeling. The model will include  $\Delta$ QTcF as the dependent variable, moxifloxacin plasma concentration as the explanatory variable (0 for placebo), centered baseline QTcF (i.e., baseline QTcF for individual subject at each post-dose time point minus the population mean baseline QTcF for all subjects in the same treatment period) as an additional covariate, treatment (moxifloxacin=1 or placebo=0) and time (i.e., post-dose time point) as fixed effects, and a random intercept and slope per subject (Garnett et al). The geometric mean of the individual  $C_{max}$  values for subjects receiving the single dose of 400 mg moxifloxacin will be determined. The predicted effect and its 2-sided 90% CI for  $\Delta\Delta$ QTcF (i.e., slope estimate × concentration + treatment effect-specific intercept) at this geometric mean  $C_{max}$  will be obtained.

If the slope of the concentration-QTc ( $\Delta$ QTcF) for moxifloxacin is statistically significant at 10% level for 2-sided test and the lower bound of the 2-sided 90% CI of the predicted effect of  $\Delta\Delta$ QTcF is above 5 ms at the geometric mean Cmax for 400 mg moxifloxacin, assay sensitivity will be deemed to have been demonstrated.

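### The primary model's non-convergence rule can end with no random effects; a simpler covariance should be tried first and a subject intercept kept as the floor (minor)

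*SAP*

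**What the plan says.** SAP 10.3.1 fits the change in QTcF on concentration, treatment, time and centred baseline, with a random intercept and slope per subject. On their covariance it states: "An unstructured covariance matrix will be specified for the random effects". The code puts this in one statement, "RANDOM INT CONC /type=UN SUBJECT=SUBJID s", and has no REPEATED statement. If convergence fails even after the concentrations are rescaled, "the random effect on the slope and intercept will be dropped, in this order, until convergence is achieved".

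The decision rule in the same section begins "If the upper bound of the 2-sided 90% CI (equivalent to the upper bound of the 1-sided 95% CI) of the predicted QTc effect" and requires that bound to lie below 10 ms.

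SAP 10.4 specifies the moxifloxacin model as similar to the primary one, with "a random intercept and slope per subject (Garnett et al"). It does not say whether the convergence rule carries over.

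For comparison, if the unstructured matrix fails in the by-time point model of SAP 10.5, other covariance structures are considered and a subject random effect is part of the model.

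**The concern.** A fallback matters only when it is invoked, but then it alone sets the interval for the primary conclusion. Two features of this one are weak.

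- It goes straight from a correlated intercept and slope to no slope. The intermediate choice, uncorrelated intercept and slope, is skipped.
- It has no floor. Once the intercept is dropped as well, nothing in the model carries within-subject correlation, and the fit is ordinary regression with independent errors.

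If subjects' slopes truly differ, a model without a random slope leaves that variation out of the standard error. The interval is then too narrow, and the error favours declaring that 10 ms is excluded. If the same rule were used for moxifloxacin, a narrow interval would favour placing the lower bound above 5 ms.

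**Working it through.** **Inputs from the documents.** 28 evaluable subjects (SAP 3.5: "It is planned to enrol up to 34 subjects to ensure 28 subjects with evaluable data"); 15 post-dose times (SAP 10.1: "0.5, 1, 1.5, 2, 2.5, 3, 3.5, 4, 5, 6, 7, 8, 12, 24, and 36 hours post-dose"); three treatments in the primary model (T, ST, P); 2-sided 90% CI; 10 ms limit. The visible text gives no variance components and no exposure variability, so these are assumed below. The plan states no coverage figure to reproduce.

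**Count.** 28 x 3 x 15 = 1,260 values (34 x 3 x 15 = 1,530 if all 34 contribute). The moxifloxacin model has 28 x 2 x 15 = 840.

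**Quantity decided on.** Effect at Cmax = treatment intercept + slope x Cmax; upper bound = estimate + t(0.95, df) x SE.

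**Hand check of the first step (slope dropped).** If slopes vary with SD w (in ms at the supratherapeutic Cmax), the mean over 28 subjects carries an extra SD of about w/√28, which the slope-dropped SE omits. In simulation A below, the slope-dropped half-width was about 0.755 ms, so SE = 0.755/1.646 = 0.459 ms. True SD = √(0.459² + w²/28); coverage = 2Φ(1.646 x 0.459/true SD) − 1.

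- w = 1: true SD 0.496, coverage 87%
- w = 2: true SD 0.594, coverage 80%
- w = 3: true SD 0.729, coverage 70%

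**Simulation A: fallback forced in every trial.** 600 trials per cell; subject SD 5 ms, residual SD 5.5 ms, exposure log-SD 0.3, half-life 6 h, true effect 6 ms, no period-level error; t with 27 df (as planned) or 1,200 df (fallbacks) in place of Kenward-Roger. Coverage of the 90% CI at the supratherapeutic Cmax, %:

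| Slope SD (ms) | As planned | Slope dropped | No random effects |
|---|---|---|---|
| 0 | 93.5 | 90.2 | 76.8 |
| 1 | 92.7 | 87.5 | 75.8 |
| 2 | 91.0 | 76.8 | 71.7 |
| 3 | 90.3 | 65.7 | 64.2 |

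Monte Carlo SE is 1.2 points at 90% and 2.0 at 60%. The slope-dropped column follows the hand check and falls somewhat below it at larger w.

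**Simulation B: the skipped step.** 400 trials per cell, the same subject, residual and exposure SDs, no period error. At slope SD 2 ms, coverage was 87.5% as planned, 88.0% with uncorrelated random effects (TYPE=VC), 74.2% with the slope dropped and 67.0% with no random effects (77.2% at slope SD 0).

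**Simulation C: false passes.** 300 trials per cell, residual SD 7 ms, true effect exactly 10 ms, no period error, slope SD 0, 1 and 1.5 ms per therapeutic-Cmax unit. The upper bound fell below 10 ms, against 5% nominal, in:

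- 3.3, 4.0 and 3.3% with both random effects
- 5.0, 16.3 and 21.3% with the slope dropped
- 15.0, 18.0 and 23.3% with no random effects

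**Sensitivity to exposure variability.** With no slope variance and no baseline covariate (2,000 trials per cell, subject SD 5, residual SD 5.5), no-random-effects coverage was 97, 94, 87, 82 and 77% at exposure log-SD 0, 0.1, 0.2, 0.3 and 0.4. Subject intercepts enter the estimate mainly through differences in exposure between subjects, so the loss appears only from about 0.2.

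**How often the rule might act.** In simulation C no optimiser failure was reported in 3 x 300 x 2 = 1,800 mixed-model fits. Taking a singular covariance fit as a stand-in trigger in simulation A, it fired in 63, 34, 6 and 0.2% of trials at slope SD 0, 1, 2 and 3 ms. Overall coverage under the rule was then 92.3, 91.8, 91.0 and 90.3%. The last step was reached in none of these 4 x 600 = 2,400 trials.

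**The case against.** The rule is prespecified, ordered and preceded by rescaling. With the stand-in trigger it acts mostly where slope variance is close to zero, and overall coverage stays at or above the nominal 90%. With subject SD 0.5-1 ms the last step was reached in 102 of 3,000 trials; 98 of these were at 0.5 ms, where the no-random-effects model still covered 90%. The low coverage figures need convergence to fail for some other reason while slopes really vary. All of this stands, and it is why the point is minor. A singular fit is not the SAP's trigger either: the SAP speaks of convergence and does not say whether singularity counts, so the firing rates do not estimate how often the rule would apply.

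It is also fair to read SAP 10.4 as inheriting the rule, since it calls the model similar and does not restate the covariance type or the degrees-of-freedom method. One added sentence would settle it.

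Three stronger readings are tempting and are not supported.

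- A reader might infer that the primary analysis will probably be run as independent-error regression. Nothing in the documents suggests that; it is the last resort of a sequence.
- A reader might infer that no sensitivity analysis protects the primary result. The SAP contents list shows redacted entries after 10.3.1, so absence cannot be claimed.
- A reader might charge this rule with error shared within a subject's period. The planned model has no such term either, so that is a separate question, and no figure here includes it.

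**Conclusion.** The concern holds as a minor flaw in wording. The visible rule allows a model with no random effects to decide the 10 ms conclusion and skips an obvious intermediate structure. If the fallback is used while slopes differ between subjects, the deciding interval is too narrow. Coverage is then roughly 65-90% with the slope dropped and 64-77% with no random effects, against about 88-93% as planned.

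These figures rest on assumed variance components, no period-level error, exposure log-SD 0.3, and fixed degrees of freedom in simulation A in place of Kenward-Roger. The no-random-effects figure is the least secure, because at low exposure variability that model is not anti-conservative. That the fallback is unlikely is a judgement supported by the simulations; the documents give no rate, and PROC MIXED itself was not tested.

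A reader might also infer that the deciding interval needs a more conservative standard error, such as the larger of a model-based and a subject-clustered one with n−1 df. That would displace the specified Kenward-Roger method. In the 380 + 203 + 35 = 618 singular trials it changed coverage by about six trials, so it is not recommended for the decision.

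**What to change.** Replace the convergence sentence in SAP 10.3.1 with:

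> If the model does not converge after rescaling, TYPE=UN will be replaced by TYPE=VC (uncorrelated random intercept and slope). If this also fails, the random slope will be removed and the subject random intercept kept as the minimum structure. A model without random effects will not be used for inference. Kenward-Roger df will be used throughout, and the structure used will be reported. The same order applies to the moxifloxacin model in 10.4.

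If the slope is dropped, a subject-clustered standard error may be reported as a sensitivity result only.

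The cost is a few sentences and no new data. The change does not remove all risk: where the unstructured fit is singular, TYPE=VC often estimates a slope SD near zero too (85, 81 and 60% of the singular trials at slope SD 0, 1 and 2 ms), and an intercept-only interval is still too narrow if slopes vary. Reporting the structure used lets a reader see when that applies.

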The relationship between plasma concentrations of ITF2357 and change-from-baseline QTcF (Δ QTcF) be quantified using a linear mixed-effects modeling approach. The model will include Δ QTcF as the dependent variable, plasma concentrations of ITF2357, as the explanatory variate (0 for placebo), centered baseline QTcF (i.e., baseline QTcF for individual subject minus the population mean baseline QTcF for all subjects in the same treatment period) as an additional covariate, treatment (active = 1 or placebo = 0), time (i.e., nominal post-dose time point) as fixed effects, and random effects on the intercept and slope per subject (Garnett et al. 2018). 11

[figure not shown]
The degrees of freedom of estimates will be determined by the Kenward-Roger method. From the model, the slope (i.e., the regression parameter for concentrations of ITF2357and the treatment effect-specific intercept (defined as the difference between active and placebo) will be estimated together with the 2-sided 90% CI. The estimates for the time effect will be reported with degrees of freedom and SE.

The geometric mean of the individual C_{max} values for subjects in each of the active dose groups will be determined. The predicted effect and its 2-sided 90% CI for $\Delta\Delta$ QTcF at this geometric mean C_{max} will be obtained. If the upper bound of the 2-sided 90% CI (equivalent to the upper bound of the 1-sided 95% CI) of the predicted QTc effect ($\Delta\Delta$ QTcF) is below 10 msec at clinically relevant plasma levels, it will be concluded that ITF2357, does not cause clinically relevant QTc interval prolongation within the observed plasma concentration ranges.

To evaluate the adequacy of model fit with respect to the assumption of linearity, the observed $\Delta QTcF$ values adjusted by population time effect estimated from the model will be used. These individual placebo-adjusted $\Delta QTcFi,k$ ($\Delta\Delta QTcFi,k$) values equal the observed individual $\Delta QTcFi,k$ for subject administered with ITF2357 or placebo at time point k minus the estimated population mean placebo effect at time point k (i.e., time effect). A quantile plot, i.e. plot of the

29-SEP-2020

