### 4. Change From the Protocol

No changes in planned analyses were done compared to the protocol.

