### 10.5 By-Time Point Analysis

The by-time point analysis for QTcF will be based on a linear mixed-effects model with  $\Delta$ QTcF as the dependent variable, period, sequence, time (i.e., nominal post-dose time point), treatment (therapeutic dose of ITF2357, supratherapeutic dose of ITF2357, moxifloxacin, and placebo) and time-by-treatment interaction as fixed effects, and baseline QTcF as a covariate. An unstructured covariance matrix will be specified for the repeated measures at post-dose time points for subject within treatment period. If the model with an unstructured covariance matrix fails to converge, other covariance matrices such as compound symmetry and autoregressive will be considered. The model will also include a subject-specific random effect. If the fixed effects for period and/or sequence should prove to be not significant (i.e., if the P value > 0.1), these effects may be removed from the model and the analysis repeated without those covariates. From this analysis, the LS mean, SE, and 2-sided 90% CI will be calculated for the contrast "TTF2357 versus placebo" ( $\Delta\Delta$ QTcF) for each dose of ITF2357 at each post-dose time point, separately.

For HR, PR, and QRS interval, the analysis will be based on the change-from-baseline postdosing values ( $\Delta$ HR,  $\Delta$ PR, and  $\Delta$ QRS). The same (by-time point analysis) model will be used as described for QTcF. The LS mean, SE, and 2-sided 90% CI from the statistical modeling for both change-from-baseline and placebo-corrected change-from-baseline values will be listed in tables and graphically displayed.

The SAS code for the by-time point analysis for QTcF is as follows.

11-JUN-2021 (Final 2.0)

PROC MIXED DATA=ECG; CLASS SUBJID TREAT TIME PERIOD SEQUENCE; MODEL DQTc=BASE TREAT TIME TREAT\*TIME PERIOD SEQUENCE/DDFM=KR; random intercept / SUBJECT =SUBJID type=UN; REPEATED TIME / SUBJECT = PERIOD\*SUBJID type = un; LSMEANS TREAT\*TIME/CL DIFF ALPHA=0.1; RUN;

Where ECG = QT/QTc population, SUBJID = subject identifier, TREAT = treatment (therapeutic dose of ITF2357, supratherapeutic dose of ITF2357, moxifloxacin, and placebo), TIME = nominal post-dose time point, BASE = baseline QTcF, PERIOD = period, SEQUENCE = sequence, and DQTc =  $\Delta QTcF$ .

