#### Italfarmaco S.p.A.

#### 16. Appendix A: Early Precision QT Analysis

Twelve-lead ECGs will be extracted in up to 10 replicates from each nominal time point prespecified in the protocol. The median value of each parameter from the set of evaluable beats in each extracted replicate will be calculated, and then the mean of all available medians (minimum 3 medians) from the nominal time point will be used as the subject's reportable value at that time point.

Early Precision QT analysis (formerly High Precision QT analysis) will be performed on all analyzable (non-artifact) beats in the 10 ECG replicates (1 replicate consists of one 14 second ECG). Statistical quality control procedures will be used to review and assess all beats and identify "high" and "low" confidence beats using several criteria including:

- QT or QTc values exceeding or below certain thresholds (biologically unlikely);
- RR values exceeding or below certain thresholds (biologically unlikely);
- Rapid changes in QT, QTc, or RR from beat to beat.

Placement of fiducials and measurements of all primary ECG parameters (QT, QTc, RR) in all recorded beats of all replicates will be performed using the iCOMPAS software. All beats that are deemed "high confidence" will not be reviewed by an ERT cardiac safety specialist. All low confidence beats will be reviewed manually by an ERT cardiac safety specialist and adjudicated using pass-fail criteria. The beats found acceptable by manual review will be included in the analysis. The beats confirmed to meet fail criteria will not be included in the analysis.

For the purpose of measuring PR and QRS intervals and to assess T-wave morphology and presence of U-waves, the TQT Plus algorithm will select the 3 ECG replicates with the highest quality score from the ECG extraction window. These 3 ECGs will be analyzed using a semi-automated process to determine these parameters. If 3 consecutive usable beats cannot be identified in at least 2 of the 3 replicates, then all beats in all replicates will be reviewed for that time point using a manual analysis.

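### The primary ITF2357 concentration-QTc model has no subject-by-period term, so its 90% CI is too narrow at the therapeutic Cmax and, depending on the variances, at the supratherapeutic Cmax

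*SAP*

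**What the plan says.** The primary model in SAP 10.3.1 regresses change-from-baseline QTcF on treatment (active or placebo), ITF2357 concentration, nominal time and centred baseline. Its random part is coded as "RANDOM INT CONC /type=UN SUBJECT=SUBJID s". PERIOD appears in neither the CLASS nor the MODEL statement, and there is no REPEATED statement. Protocol 12.4.1 agrees, giving "random effects on the intercept and slope per subject".

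If the model does not converge after the concentrations are rescaled, SAP 10.3.1 says "the random effect on the slope and intercept will be dropped, in this order, until convergence is achieved". Nothing is put in their place.

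Three other places bear on this:

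- SAP 10.2.2: "baseline is defined as the average of the measured ECG intervals from the 3 ECG time points", taken separately in each period.
- SAP 10.5, for the same dependent variable: "An unstructured covariance matrix will be specified for the repeated measures at post-dose time points for subject within treatment period", coded with subject crossed with period as the grouping.
- SAP 10.4: the moxifloxacin model is described as similar to the primary one, with "a random intercept and slope per subject".

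**The concern.** Every change within a period carries the error of that period's baseline, plus any shift in the subject's QTcF that day that differs between pre-dose and post-dose. Given only a subject intercept and slope, the primary model treats the 15 readings of a period as independent. It therefore counts a period-level error as if it averaged out over 15 readings. The baseline covariate absorbs only part of that error. Kenward-Roger adjusts for estimating the variance components in the model; it cannot supply one that was left out. The secondary by-time-point model does allow for this dependence.

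The QT conclusion rests on the upper 90% bound at each dose group's geometric mean Cmax lying below 10 ms, which the SAP equates with a one-sided 95% bound. If the standard error is too small, the 5% risk of wrongly excluding an effect is not the real risk.

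The fallback raises a separate problem. Without the random slope, the model ignores slope differences between subjects as well as period error. Without both terms, all 3 × 15 = 45 readings per subject count as independent.

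**Working it through.** **Plan's own figure.** None can be reproduced. Protocol 8.1.1 and SAP 10.8 appear in the public text as headings only, so no variance, power or CI width for the primary model is visible. What can be read is 28 evaluable of up to 34 enrolled.

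**Inputs from the documents.** 28 subjects; three periods (P, T, ST) for ITF2357 and two (P, M) for moxifloxacin; three pre-dose and 15 post-dose readings per period; 90% two-sided CI; margins of 10 ms and 5 ms. Each reading averages up to 10 replicates; Appendix A says "the mean of all available medians (minimum 3 medians) from the nominal time point will be used".

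**Assumed inputs.** Reading SD 2.5–5 ms; subject-by-period SD 1–4 ms; extra post-dose period shift SD 0–2 ms; AR(1) correlation 0 or 0.5; slope CV 0 or 30% (20% for moxifloxacin); between-subject SD 15 ms; one-compartment profiles with ST = 3 × T; half-life 6 h (ITF2357) and 12 h (moxifloxacin); exposure CV about 30%.

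**Orientation by hand.** Take the plain mean difference between one active period and placebo. A period-level error with SD s adds 2s²/28 to its variance, however many readings there are. Treated as independent reading noise, it is credited with only 2s²/(28 × 15). With reading SD 4 ms and three baseline readings, s = 4/√3 = 2.31 ms before the baseline covariate takes its share:

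- true contribution: √(2 × 5.33/28) = 0.62 ms
- contribution counted: √(2 × 5.33/420) = 0.16 ms

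The covariate and the random slope absorb some of this, so the net effect needs simulation.

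**Simulation.** I generated raw QTcF, formed changes from the period baseline and fitted each model by REML. There were 500 runs per setting (simulation SE about 1.5 points), with nine settings for ITF2357 and five for moxifloxacin. A t quantile with 27 df stood in for Kenward-Roger throughout. One-sided error means the upper bound lying below the true effect (ITF2357) or the lower bound lying above it (moxifloxacin); nominal is 5%.

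| Model | Result | T Cmax | ST Cmax | Moxifloxacin |
|---|---|---|---|---|
| As written | 90% CI coverage | 57–78% | 81–89% | 90–94% |
| As written | one-sided error | 12–22% | 5–11% | 2–7% |
| Plus subject-by-period intercept | coverage | 89–91% | 87–92% | 86–92% |
| Plus subject-by-period intercept | one-sided error | 4–7% | 4–7% | – |
| Fallback, slope dropped | coverage | – | 37–62% | 38–46% |
| Fallback, slope dropped | one-sided error | – | 20–33% | 26–33% |
| Fallback, no random effects | coverage | – | 36–64% | 39–49% |

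At T, the model SE was 0.20–0.50 ms against a true SD of 0.37–1.02 ms. At the upper ends, the bound is too low by 1.703 × (1.02 − 0.50) = 0.89 ms. With baseline error alone (no extra shift), coverage was still 58–78% at T and 81–89% at ST. T suffers more because the random slope absorbs much of the ST-period deviation but little of the T-period deviation.

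**Sensitivity to the simulation design.** A second simulation (residual SD 6 ms, subject-by-period SD 0–6 ms, 200–600 runs per setting) gave T coverage of 60–82% and one-sided error of 10–19% for subject-by-period SD of 2 ms or more. At ST it gave 84–91% and 5–9% for SD of 1–6 ms. A third (raw QTcF, baseline centred either way, 200 runs per setting) gave 56–78% at T and 79–93% at ST, rising to 87–95% and 88–93% with the added term.

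**Fallback trigger.** The fitted unstructured matrix was singular in 0–1% of runs.

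**The case against.** - **The variances are redacted, not omitted.** This is right, and every percentage here is conditional on assumed values. Redacted text after SAP 10.3.1 may also hold further model checks. The primary code, however, is visible and complete.
- **The T result needs period variance.** In the second simulation, with subject-by-period SD set to zero, model SE over true SE was 0.89–0.95, and at 1 ms it was 0.87, so there the shortfall is small. But zero there also means no shared baseline error, which is implausible for a baseline measured afresh in each period. If the baseline covariate absorbs more than I assumed, T coverage moves toward nominal; other runs gave 63–89%.
- **The effect in milliseconds is small.** This stands. With a non-negative slope, the ST bound will normally decide the verdict, and there the fix barely changes the width.
- **The fallback is remote.** This also stands. Rescaling is required first, singularity is only a proxy for non-convergence, and the fallback figures come from forcing it on data the full model can fit. Its use for moxifloxacin is inferred from the reference to a similar model in SAP 10.4.
- **The remedy may fall short.** One side setting restored the SE only partly (ratio 0.57–0.64), and a smaller run of 150 per setting gave 83–91% at T and 81–86% at ST. The larger runs, and the run under both centrings, did not reproduce this.
- **Protocol and SAP agree on the model and cite a published paper for it.** That agreement does not give the interval its stated error rate in this three-period dataset.

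**Conclusion.** The concern holds. As specified, the primary model understates the standard error at the therapeutic Cmax in every setting tried with a shared period error. At the supratherapeutic Cmax, the shortfall ranges from negligible to moderate, depending on variances the public text does not show. The upper bound is too low by up to about 0.9 ms at T and 0.6 ms at ST, so the conclusion is at risk only if a bound lies within about 1 ms of 10 ms. The moxifloxacin assay-sensitivity interval is not too narrow under the model as written.

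The fallback is a contingency. If it were used, the 10 ms exclusion would lose its stated error rate; so would the 5 ms moxifloxacin criterion if the fallback were applied there.

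The structural gap is certain. The sizes rest on the assumed variances and concentration profiles, and on the 27-df stand-in for Kenward-Roger.

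**What to change.** 1. In SAP 10.3.1, add PERIOD to the CLASS statement and a second line, `RANDOM INT / SUBJECT=PERIOD*SUBJID`, keeping the subject intercept and slope. An autoregressive structure is not a substitute, because a shared baseline error does not decay with time. A fixed PERIOD effect is optional.
2. Replace the fallback. First simplify the unstructured matrix to a diagonal one (simulated coverage 89–91% at T, 87–92% at ST). If that also fails, remove only the random slope, keep both intercepts, and report sandwich standard errors clustered on subject, with degrees of freedom based on the number of subjects. That gave 85–90% at ST and 86–89% for moxifloxacin; the same model without sandwich errors gave 70–90% at ST.
3. In SAP 10.4, the added term is optional, for consistency only. It is not needed to correct the moxifloxacin interval, and simulated coverage was slightly lower with it.
4. Record the change in SAP Section 4, which now reads "No changes in planned analyses were done compared to the protocol", since Protocol 12.4.1 lists only subject-level random effects.

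The cost is one code line, one CLASS variable, one SAP paragraph and the sponsor approval that SAP Section 1 requires; no new data. The CI half-width grows by about 0.2–0.8 ms at T and changes by −0.1 to +0.2 ms at ST. Running the added term only as a sensitivity analysis would be easier to agree, but would leave the deciding bound with the wrong error rate.
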